9.3.1 Unscheduled Visit

An unscheduled visit can be held at any time during the study, if deemed necessary by the investigator. In addition, an unscheduled visit must be scheduled to occur as soon as possible if an AESI is reported during any telephone contact. An unscheduled visit will not replace any of the above visits as per schedule of events. Assessments performed at an unscheduled visit

will be at the investigator's discretion, but should include AE assessment, AESI query, concomitant medication and possibly FWS.

In case of an unscheduled visit, the investigator should complete the "Unscheduled Visit Form" in the CRF.

9.4 Subject Diary and Patient Reported Outcomes

9.4.1 Subject Diary

A paper subject diary will be provided to each subject at the baseline visit (day 0) and one week after the first treatment visit to record the following information:

Daily documentation of FWS score at maximum frown.

The subject diary will be collected at the visit one week after the first treatment and the subject will be given a second diary to be returned at the visit two weeks after the first treatment. Subjects will be trained on use of the diary during the baseline visit (training will be recorded in the source).

Treatment onset will be evaluated by the subject and the investigator (using FWS) at study visits one, two and four weeks after the first treatment and documented accordingly. In addition, for further determining onset of treatment, the subject will record the FWS score in diaries daily for the first two weeks after treatment (in the first treatment cycle).

The subject diary will serve as a source record and remain at the study site. Entries in the subject diary will be transcribed into the electronic data capture (EDC) system by the blinded member of the site study team.

9.4.2 Patient Reported Outcomes

A patient-reported outcome (PRO) instrument (i.e. a questionnaire plus the information and documentation that support its use) is a means to capture patient, or subject views of outcomes used to measure treatment benefit or risk in IMP clinical trials. Three PRO instruments will be used in this study to support claims in the product label, comprising:

- The FWS, which will be used to evaluate the severity of glabellar lines (Section 20.1 and Section 10.1) which will be completed by the subject (PRO; Glabellar Line Scale for Subjects, GLS-S) and the investigator (clinician reported outcome; Glabellar Line Scale for Investigators, GLS-I).
- The modified Skindex-16 (GL-QoL) and FACE-Q scales (Appraisal of Lines Between Eyebrows scale and Age Appraisal VAS), which will be used to measure the psychological impact of glabellar lines and concerns relating to their glabellar lines, respectively (Section 20.3 and Section 20.4, Section 20.5).

• The FACE-Q Satisfaction with Outcome Scale which will be used to measure subject satisfaction with treatment (Section 20.6).

Entries in the questionnaires will be transcribed into the EDC system by a blinded member of the site study team.

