5.3 Secondary Objectives

- 1. To assess the proportion of responders at maximum frown and at rest at various time points after each treatment, based on investigator and subject assessments.
- 2. To assess the psychological impact of BoNT/A-DP treatment on subjects (in terms of emotional and social functioning and concerns relating to their glabellar lines) in comparison with placebo after a single treatment.
- 3. To assess onset of effect and the duration of effect (at maximum frown) after a single treatment with BoNT/A-DP compared with placebo (first treatment cycle), based on investigator and subject assessments.
- 4. To provide long term safety data of BoNT/A-DP based on multiple treatment cycles and to establish a sufficient safety database to support regulatory approval.
- 5. To assess subject perceptions of effect of, and satisfaction with, treatment in comparison with placebo (first treatment cycle) and during the open-label extension phase.

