6.4.2.2 Additional Secondary Endpoints

- 2. The percentage of responders at maximum frown (as defined in 6.4.1.1) at week 12 (after the first treatment with BoNT/A-DP or placebo).
- 3. The percentage of responders at week 16 (after the first treatment).
- 4. The percentage of responders at week 20 or later (after the first treatment).

- 5. The proportion of subjects with a ≥ 1 point reduction in FWS score at rest at week 4 in the first treatment cycle, based separately on the investigators' and the subjects' in-clinic assessments (applicable only for subjects who have a FWS score at rest ≥ 1 at baseline).
- 6. The proportion of responders among BoNT/A-DP and placebo groups with a FWS score of 0 or 1 and an improvement ≥ 2 points in FWS score (at maximum frown) during the first treatment cycle visit relative to baseline, based on both the investigator's and the subject's in-clinic assessments (composite endpoint, at weeks 1, 2 and 8).
- 7. The proportion of subjects with ≥ 2 point and ≥ 1 point reduction in FWS score (at maximum frown) in the BoNT/A-DP and placebo groups during the first treatment cycle visit relative to baseline, based on the independent rater's assessment of photographs (at baseline and visits 2, 4, 12, 16 and 20 weeks after treatment, within the first treatment cycle).
- 8. Time to onset of effect in the BoNT/A-DP and placebo groups in the first treatment cycle, as measured at weeks 1, 2 and 4 based separately on subject and investigator assessments. Onset of effect defined as at least a 1 point improvement in FWS score from baseline (at maximum frown). In addition, onset of effect will be assessed by subjects daily in the first 2 weeks after treatment, by recordings in the subject diary.
- 9. The extent of subject perceptions of effect of, and satisfaction with, treatment, in the BoNT/A-DP and placebo groups, during each treatment cycle, as assessed by the FACE-Q Satisfaction with Outcome Scale.
- 10. The proportion of subjects with a ≥ 1 point reduction in FWS score at rest in the BoNT/A-DP and placebo groups, relative to baseline, during the first treatment cycle, based on the independent rater's assessment of photos.
- 11. The percentage of subjects with a FWS score of 0 or 1 and an improvement of ≥ 2 points in FWS score at maximum frown (investigator and subject assessment) at 4 weeks after re-treatment relative to the rating at the preceding end of cycle visit.

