12.4.2 Secondary Outcome Measures

Key Secondary Analyses:

The testing of the key secondary endpoint will be performed with appropriate multiplicity control based on the FAS population. The results of each test result will only be considered confirmative if the previous test in the order showed a confirmatory result at a one-sided significance level of 0.025. If the one-sided p-value is larger than 0.025 for any of the tests, the results of the subsequent tests will only be considered exploratory, and not confirmatory. The application of this hierarchical approach keeps the global significance level to 0.025 one-sided and requires no further adjustment of the significance level.

The following order of tests will be defined:

- Primary endpoint (composite endpoint)
- Key secondary endpoint 1
 - 1.1: The modified Skindex-16 (GL-QoL) Emotional domain
 - 1.2: The modified Skindex-16 (GL-QoL) Social Functioning domain
 - 1.3: The modified Skindex-16 (GL-QoL) Overall score
 - 1.4: The FACE-Q Appraisal of Lines Between Eyebrows scale
 - 1.5: The FACE-Q Age Appraisal VAS score

Analysis of key secondary endpoint 1: The extent of change in psychological impact (emotional and social functioning, and concerns relating to glabellar lines) at week 4 after the first treatment, in the BoNT/A-DP group in comparison with placebo, relative to baseline, as assessed by the modified Skindex-16 (GL-QoL) and the FACE-Q Appraisal of Lines Between Eyebrows and FACE-Q Age Appraisal VAS.

The modified Skindex-16 (GL-QoL) and FACE-Q Appraisal of Lines Between Eyebrows scale and FACE-Q Age Appraisal VAS will be analyzed according to the foreseen analysis approach of these tools, as described below.

Emotional and Social Functioning

The modified Skindex-16 (GL-QoL) Emotional and Social Functioning domains and overall scores will be derived in accordance with the Skindex-16 manual, adapted for the GL-QoL. The scores will be standardized on a scale from 0 (no impact) to 100 (maximal impact); a scale score is the average of responses to items addressing a construct. Domain and overall scores will be calculated if at least two of three social and of at least two of four emotional domain items are present. The absolute change from baseline (measured on the screening visit) will be calculated for the domain and overall scores and statistically compared between the treatment groups using the Wilcoxon Rank Sum test (or t-test). Estimates of 'mild',

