2.2 Secondary Objectives

1. To assess the proportion of responders at maximum frown and at rest at various time points after each treatment, based on investigator and subject assessments.
2. To assess the psychological impact of BoNT/A-DP treatment on subjects (in terms of emotional and social functioning and concerns relating to their glabellar lines) in comparison with placebo after a single treatment.
3. To assess onset of effect and the duration of effect (at maximum frown) after a single treatment with BoNT/A-DP compared with placebo (first treatment cycle), based on investigator and subject assessments.
4. To provide long term safety data of BoNT/A-DP based on multiple treatment cycles and to establish a sufficient safety database to support regulatory approval.
5. To assess subject perceptions of effect of, and satisfaction with, treatment in comparison with placebo (first treatment cycle) and during the open label extension phase.

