8.6.1.1 Multiplicity

The testing of the primary and the key secondary efficacy endpoints will be performed with appropriate multiplicity control based on the FAS population. The results of each test will only be considered confirmative if the previous test in the order showed a confirmatory result at a one-sided significance level of 0.025. If the one-sided p-value is larger than 0.025 for

Statistical Analysis Plan (SAP)

CROMA
est. 1976

any of the tests, the results of the subsequent tests will only be considered exploratory, and not confirmatory. The application of this hierarchical approach keeps the global significance level to 0.025 one-sided and requires no further adjustment of the significance level.

The following order of tests will be applied:

- Primary endpoint (composite endpoint)
- Key secondary endpoint 1
 - 1.1: The modified Skindex-16 (GL-QoL) Emotional domain
 - 1.2: The modified Skindex-16 (GL-QoL) Social Functioning domain
 - 1.3: The modified Skindex-16 (GL-QoL) Overall score
 - 1.4: The FACE-Q Appraisal of Lines Between Eyebrows scale
 - 1.5: The FACE-Q Age Appraisal VAS score

All other analyses (e.g., additional analyses of the primary and the key secondary efficacy endpoints using other analysis populations or other statistical methods, analyses of additional secondary endpoints) will only be considered exploratory.

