- of subjects with an improvement of ≥ 2 points in FWS at maximum frown at 4 weeks after re-treatment,
- of subjects with ≥ 1 point reduction in FWS score at maximum frown (at weeks 1, 2, 4, 8, 12, 16 and 20 relative to baseline,
- of subjects with ≥ 1 point reduction in FWS score at maximum frown at week 4 relative to re-treatment baseline,

the CMH test (with stratification variable site) and the Pearson χ^2 -test will be applied. In case of a total number of observations below 30, or in case of at least one cell frequency below 5, Fisher's exact test will be used instead of the χ^2 -test. Two-sided 95% CIs for response rates will be calculated, where appropriate. Additionally, the cumulative proportions of effects at weeks 1, 2, and 4 will be calculated.

Time to onset of effect in the first treatment cycle will be analyzed descriptively and by using the Kaplan-Meier method. Moreover, the daily assessments of the line severity when frowning will be analyzed descriptively. The FACE-Q satisfaction with outcome scale will be analyzed descriptively.

All efficacy endpoints, with the exception of “responder” 4 weeks after re-treatment, will be analyzed for the first treatment cycle only. The analysis of “responder” 4 weeks after re-treatment will be conducted on observed values only, i.e., subjects with missing investigator or the subject in-clinic assessments on FWS week 4 or at the preceding end of the cycle visit will be excluded from analysis. Subjects who were treated with placebo during the first treatment cycle are excluded from the analysis of this endpoint, but not assigned as being non-responders. A two-sided McNemar test (using a significance level of 0.05) will be used to compare the response proportions between week 4 re-treatment visit and at the preceding end of the cycle visit. These endpoints will be separately analyzed for each open label extension cycle.

In addition to the FAS population, the analyses of these endpoints will also be based on the MFAS and PP populations. For all analyses, a one-sided significance level of 0.025 will be used, if not stated otherwise. Additional exploratory subgroup analyses will be conducted as described in Section 8.8.

Statistical Analysis Plan (SAP)

CROMA
est. 1976

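### FACE-Q Satisfaction with Outcome is named as support for label claims and an objective asks for a placebo comparison, but only descriptive summaries by arm are planned, so the trial cannot conclude superiority on it

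*Protocol*

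**What the plan says.** Protocol 9.4.2 introduces a list of patient-reported instruments with "Three PRO instruments will be used in this study to support claims in the product label, comprising". The third entry is "The FACE-Q Satisfaction with Outcome Scale which will be used to measure subject satisfaction with treatment".

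The objective that matches it is number 5, in Protocol 5.3 and again in SAP 2.2: "To assess subject perceptions of effect of, and satisfaction with, treatment in comparison with placebo (first treatment cycle) and during the open label extension phase". The endpoint is additional secondary endpoint 9 (Protocol 6.4.2.2, SAP 4.3). It covers both arms, in each cycle, "as assessed by the FACE-Q Satisfaction with Outcome Scale".

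The confirmatory order in Protocol 12.4.2 and SAP 8.6.1.1 and 8.6.3 is the primary endpoint followed by steps 1.1 to 1.5. The last entry is "1.5: The FACE-Q Age Appraisal VAS score".

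For the Satisfaction scale SAP 8.6.4 says: "The FACE-Q satisfaction with outcome scale will be analyzed descriptively". Protocol 12.4.2 says the same, and SAP 8.9 repeats it for the interim analysis. On everything outside the sequence, SAP 8.6.1.1 ends: "analyses of additional secondary endpoints) will only be considered exploratory".

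**The concern.** The stated purpose of the scale and its planned analysis do not match. A sponsor that intends to support a label claim with an instrument, and sets a placebo comparison as an objective, would normally prespecify the inference that lets it make that comparison. Here the data are collected under randomised, blinded conditions, yet no result on this scale could lead to a confirmed statement of superiority. If a test were wanted later, it would be post hoc, because the double-blind data are unblinded at the interim analysis.

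**Working it through.** **Passages side by side.** Each item listed in Protocol 9.4.2, against where it is tested:

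| Item | Between-arm test | In the fixed sequence |
|---|---|---|
| FWS, subject and investigator | Yes, CMH test | Yes, as the primary composite |
| GL-QoL; FACE-Q Appraisal of Lines; FACE-Q Age Appraisal VAS | Yes, Wilcoxon (or t-test for GL-QoL) | Yes, steps 1.1 to 1.5 |
| FACE-Q Satisfaction with Outcome | None | No |

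**Are the data there?** Yes. Protocol 2.1 and 10.3 schedule the scale 4 weeks after each treatment and at the end of each cycle, in both arms in cycle 1. There is no pre-treatment assessment, so a comparison must use the score itself and not a change. Week 4 is the suitable visit because it is fixed. The end of cycle 1 depends on when each subject qualifies for re-treatment and so can fall at different times in the two arms.

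**What would a last step do to the error rate?** In a fixed sequence, a false confirmatory result requires rejecting the first true null hypothesis, which has probability at most 0.025. A step placed after 1.5 does not alter whether any earlier step is reached or rejected. The global level stays at 0.025 one-sided and the earlier tests keep their power.

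**Would such a step have useful power?** The documents give no SD, expected difference or power for this scale, so there is no figure of the plan's to reproduce. The calculation below is an illustration.

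- From Protocol 12.1 and SAP 5: 353 enrolled, 15% drop-out, 353 × 0.85 = 300.05, split 3:1 as n1 = 225 and n2 = 75.
- From SAP 8.6.1.1: one-sided 0.025, critical value 1.960.
- Assumed: a normal shift of d standard deviations; efficiency of the Wilcoxon test relative to the t-test 0.955.

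Power = Φ(d × √(0.955 × n1 × n2 / (n1 + n2)) − 1.960)

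- n1 × n2 / (n1 + n2) = 225 × 75 / 300 = 56.25
- √(0.955 × 56.25) = √53.72 = 7.33

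| Assumed d | d × 7.33 − 1.960 | Power |
|---|---|---|
| 0.3 | 0.24 | 59% |
| 0.4 | 0.97 | 83% |
| 0.5 | 1.70 | 96% |

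Power of 90% needs d = (1.960 + 1.282) / 7.33 = 0.44. These are marginal figures. As the test counts only after steps 1.1 to 1.5 succeed, the chance of a confirmatory result on satisfaction cannot exceed them.

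**The case against.** The strongest case on the other side is that the plan is consistent and deliberate. Protocol and SAP agree on the descriptive analysis throughout. Protocol section 19 shows that other endpoints were moved out of key secondary status, so the confirmatory list was reviewed and kept short. The label-claim sentence sits in a procedures section, is loosely drafted (it includes the investigator's rating under patient-reported instruments), and states no satisfaction claim, time point or comparison. Nothing in the documents requires every supporting instrument to have its own controlled test. All of this stands, and it is why this is an improvement to the plan and not an error in its confirmatory analysis. It does not remove the mismatch between the sentence in 9.4.2 and the analysis planned.

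A reader might infer that objective 5 has no analysis at all. The documents do not support that. SAP 8.1 presents summaries by treatment group, and SAP 8.9 plans the descriptive analysis of this scale at the interim, so a randomised comparison by arm will be shown. The objective is to assess, and only the inferential test is absent.

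A reader might also infer that the family-wise error rate is inflated. It is not. No test of this scale outside the sequence is planned, and SAP 8.6.1.1 would class one as exploratory.

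In the other direction, Protocol 12.4.2 and SAP 8.6.4 say in general terms that additional secondary endpoints get a suitable method for comparing the arms, and SAP 8.6.4 sets a default one-sided level. This might be read as supplying a test. However, the tests named in SAP 8.6.4 attach to a list of proportions that omits this scale, and the sentence specific to the scale says descriptive.

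**Conclusion.** The point holds in limited form. For one of the three items listed as supporting label claims, and for the placebo comparison in objective 5, the plan provides a description by arm but no basis for concluding that satisfaction is better than placebo. Error control, sample size and the primary and key secondary conclusions are unaffected.

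The absence of a test rests on the text alone and needs no assumption. The view that a last step would be worthwhile rests on the assumed shifts above: power is adequate from roughly 0.4 SD and weak at 0.3 SD.

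The documents do not show whether the interim unblinding has taken place. SAP 3.3 already describes the March to May 2020 treatment hold in the past tense, so timing must be confirmed before the fix is chosen.

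**What to change.** Before the interim unblinding, add a final step to SAP 8.6.1.1 and 8.6.3 and to Protocol 12.4.2:

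- **1.6:** FACE-Q Satisfaction with Outcome score at cycle 1 week 4, BoNT/A-DP versus placebo, FAS, Wilcoxon rank-sum test in the direction of higher satisfaction, one-sided 0.025, confirmatory only if steps 1.1 to 1.5 all succeed.
- State that the score and any missing items are handled by the developers' rules. The visible scoring appendices (B and C) cover only the other scales; this may be due to removed text, so check before adding.
- Amend the descriptive-only sentences in Protocol 12.4.2 and SAP 8.6.4 and 8.9 to except this comparison. Keep all other visits and cycles descriptive.

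The cost is one extra test on data already scheduled and its scoring specification, with no change to sample size. The drawback is that the satisfaction conclusion depends on every earlier step succeeding.

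If unblinding has already occurred, or the sponsor does not want the step, remove the scale from the label-claim sentence in Protocol 9.4.2 and word the comparison in objective 5 (Protocol synopsis and 5.3, SAP 2.2) as descriptive.

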9.5 Subject Completion/Discontinuation

A subject is considered to have completed the study when he/she ceases active participation in the study because the subject has, or is presumed to have, followed all appropriate conditions of a protocol (with or without protocol deviations). Completion of the first cycle and the open label cycles will be documented on two different CRF pages.

Subjects will be considered to be "per protocol completers" of Cycle 1 if they had no major protocol deviations in the first cycle and an in-clinic assessment with the FWS by the investigator and the subject at baseline (day 0) and at the week 4 visit were performed.

Subjects will be considered to be "per protocol completers" of the study if they have completed the final cycle within week 48-60, without major protocol deviation.

Reasons for completion or non-completion will be reported on the Completion/Termination CRF, including: completed, screen failure, premature termination due to AE (including death), discontinuation by subject(e.g.dropout, lost to follow-up, withdrawn informed consent), physician decision (e.g.non-compliance with protocol, or for safety reasons), study terminated by Sponsor, or other reason to be specified by the investigator. Regardless of the reason for subject withdrawal, all data available for the subject up to the time of completion/discontinuation should be transferred from the subject records on the appropriate CRF.

Every effort will be made to have discontinued subjects complete the End of Study visit. All procedure and assessment results performed at such visits will be recorded under the Termination visit assessments. If a subject terminates participation in the study during or after a visit and does not return for a Completion/Termination visit, or is lost to follow up their last recorded assessments shall remain under the last visit they attended (i.e. no assessment data shall be recorded under/transferred to the Completion/Termination visit assessments). The reason for discontinuation will be recorded on the CRF.

9.6 Procedures for Monitoring Subject Compliance

All study procedures are to be performed under supervision at the study site, and thus, no separate procedures will be used to monitor subject compliance.

10. ASSESSMENT OF EFFICACY

10.1 Assessment of Glabellar Line Severity: Facial Wrinkle Scale

In accordance with FDA Guidelines for Upper Facial Lines, efficacy will be determined using well defined, valid and reliable clinician-reported and subject-reported assessments, capable of measuring the critical outcomes that contribute to a conclusion of overall success or failure. For both investigator and subject assessment, measurements will be made at maximum frown (which represents the worst appearance of upper facial lines with maximum load on the muscle) and at rest (which represents the best appearance of upper facial lines with the least load on the muscle), which allows one to impute benefit when the face is in dynamic motion (variable load on the muscle).

The scale used most frequently in clinical studies is the FWS, which is a four-point rating scale as follows: 0 = no facial wrinkles; 1 = mild facial wrinkles; 2 = moderate facial wrinkles; and 3 = severe facial wrinkles. The scale has been validated and shown to be reproducible ⁴². However, this scale includes pictures at rest and at maximum frown within the one scale, meaning that the sensitivity of the scale at rest is low. The instrument proposed for use in this study is the FWS, which is named Glabellar Line Scale for Investigators [GLS-I] and Glabellar Line Scale for Subjects [GLS-S], as described in Section 20.1. The scale and the proposed instructions for its use by investigators and subjects are described in Section 20.1 and in the completion manuals: 'Glabellar Line Scale – Subject: Completion Manual', 'Glabellar Line Scale – Investigator: Completion Manual'.

